Enrollment	Point/time of patient entry into the study at which informed consent must be obtained (e.g., prior to starting any of the procedures described in the protocol)
Epoch	A part of the study which serves a specific purpose. Typical epochs are: screening, treatment, and follow-up
Medication number	A unique identifier on the label of each investigational drug package
Patient number	A unique number assigned to each patient upon signing the informed consent
Personal data	Patient information collected by the investigator that is transferred to Novartis for the purpose of the clinical study. This data include patient identifier information, study information, and biological samples
Randomization number	A unique identifier assigned to each randomized patient, corresponding to a specific treatment arm assignment
Study drug/treatment	Any single drug or combination of drugs administered to the patient as part of the required study procedures; includes investigational drug(s), placebo/comparator active drug run-ins or background therapy
Study treatment discontinuation	Point/time when the patient permanently stops taking study treatment prior to the defined study treatment completion date
Variable	A measured value or assessed response that is determined in specific assessments and used in data analysis to evaluate the drug being tested in the study
Withdrawal of consent	Withdrawal of consent from the study occurs only when a patient does not want to participate in the study any longer, and does not allow any further collection of personal data

Protocol amendments

Protocol Amendment 02 of 26-Sep-2019

Amendment rationale

[figure not shown]
Amendment 02 was implemented to provide additional details for the statistical analysis and increase the patient recruitment rate by loosening one inclusion criterion.

The study is currently ongoing. The changes were made mainly to improve the understanding and execution of the protocol and will not have an impact either on the patients' safety or on the objectives of the study.

Changes to the protocol

Changes to specific sections are shown in the track changes version of the protocol using strike through red font for deletions and red underlined for insertions.

The following modifications were made to the protocol:

- The glossary of terms was updated with new definitions of personal data and withdrawal of consent
- Clarification was added that subjects who discontinue the study during the Follow-up Epoch will have all assessments of end of study (EOS) performed
- Inclusion criterion 3 was modified by allowing earlier episodes of mild psoriasis resolved spontaneously within 6 months. The reason for this change was that some subjects did not proceed into screening because they could have had symptoms of psoriasis previously, but without a proper diagnosis. In consensus with medical experts, subjects with such a history would not change the scientific value of the study, nor the study population, and hence this inclusion criterion was slightly loosened to improve study recruitment
- Withdrawal of consent language was modified to align with the requirements of the General Data Protection Regulation
-  Additionally, clarification was provided that physical examination at Week 104 has to be recorded in the source documents at the site
- [Table 6-3](#) was updated with the definition of EOS
- The hypothesis testing for the efficacy analyses was modified to 1-sided tests at 2.5% significance level instead of 2-sided at 5% significance level
- Age and body mass index were included as covariates for the analyses

- The Wald test was replaced by the Fisher's exact test, which is mainly used when the sample size is small or the proportions are extreme. This study is of adequate size and the Wald test was proposed. However, responses for the key secondary endpoint are expected to be low; therefore, it was decided that the Fisher's exact test is more appropriate
- Clarification was added that missing data for the primary endpoint and the key secondary endpoint will be imputed with modified multiple imputation method
- The power of the key secondary endpoint was re-assessed after considering dropout rates
- The assumptions for the sample size calculations were modified. The power calculations for the primary endpoint are now based on the asymptotic Wald test instead of on the Fisher's exact test, as the accuracy of the Wald test increase in larger sample sizes and adequate response rates (which are expected for the primary endpoint). The software for the calculation was modified from nQuery Advisor® 7.0 to PASS 11

IRBs/IECs

A copy of this amended protocol will be sent to the Institutional Review Board (IRBs)/Independent Ethics Committee (IECs) and Health Authorities.

The changes described in this amended protocol are substantial and require IRB/IEC approval prior to implementation.

The changes herein affect the study-specific model ICF and the sub-study ICF.

Protocol Amendment 01 of 11-Apr-2017

Amendment rationale

The purpose of the amendment was to address requests from health authorities and to include modifications for improvement of the clarity of the protocol.

[figure not shown]
In addition, the upper limit of the age range was changed to better reflect the patient population and improve study recruitment.

Changes to the protocol

Changes to specific sections are shown in the track changes version of the protocol using strike through red font for deletions and red underlined for insertions.

The following modifications were made to the protocol:

- The investigator's global assessment mod 2011 was included as additional secondary and exploratory objectives
■ [REDACTED]
- The upper limit of the age range for inclusion of patients in the study was changed from 40 years to 50 years

[figure not shown]

- The risks-benefit section was updated with information on risks for secukinumab, biopsies and others
- The exclusion criterion involving barrier methods of contraception was modified to include applicable countries beyond the UK
- The optional use of calcipotriol 50 µg/g and betamethasone 0.5 mg/g with nb-UVB was further clarified
- The number of patients per group in the Mechanistic Sub-study was reduced from 15 to 12
- The number of biopsies to be taken from lesional or resolved skin and from never-lesional skin was corrected

[figure not shown]
Protocol summary

Protocol number	CAIN457A2322
Title	A randomized, multicenter Study to evaluate the Effect of secukinumab 300 mg s.c. administered during 52 weeks to patients suffering from new-onset moderate to severe plaque Psoriasis as early Intervention compared to standard treatment with narrow-band UVB (STEPIn study)
Brief title	Study of the efficacy of early intervention with secukinumab 300 mg s.c. compared to narrow-band UVB in patients with new-onset moderate to severe plaque psoriasis
Sponsor and clinical phase	Novartis Phase IV
Investigation type	Drug
Study type	Interventional
Purpose and rationale	The purpose of this study is to determine whether early intervention with subcutaneous (s.c.) secukinumab 300 mg in patients with new-onset moderate to severe plaque psoriasis may lead to prolonged symptom-free periods by preventing reactivation of old lesions or ultimately totally hindering the occurrence of new lesions, i.e., changing the natural course of the disease (Main Study).
Primary objective	To demonstrate that early treatment with secukinumab 300 mg s.c. (Arm A1) is superior to standard of care treatment with nb-UVB (Arm B1) in patients with new-onset moderate to severe plaque psoriasis with respect to patients achieving $\geq 90\%$ improvement (reduction) in psoriasis area and severity index (PASI 90) response at Week 52.
Secondary objectives	
Key secondary objective
 
To evaluate the superiority of early treatment with secukinumab (Arm A1) versus nb-UVB (Arm B1) based on the proportion of all randomized patients who achieve at least PASI 90 at Week 104.
 
Additional secondary objective
 
To evaluate the effects of early treatment with secukinumab (Arm A1) compared with nb-UVB (Arm B1) based on the proportion of all randomized patients who achieve at least investigator's global assessment (IGA mod 2011) 0/1 response at Week 52.

Study design	The design consists of the Main Study involving all patients in Arms A1 (A1a and A1b) and B1 (B1a and B1b) and a Mechanistic Sub-study, which comprises 5 treatment arms (A1b, A2, B1b, C1, and C2). The Main Study will be multicenter, randomized, 2-treatment-arm (secukinumab and nb-UVB), parallel-group and open-label.


Population
	
The overall study population (Main Study and Mechanistic Sub-study) will consist of a total of 196 male and female patients aged between 18 and 50 years inclusive.
 
Main Study
 
The Main Study will be conducted in patients with new-onset moderate to severe plaque psoriasis not previously treated with any systemic treatment or phototherapy.
 
A total of 160 patients will be randomized to Arm A1 or Arm B1 in approximately 75 sites worldwide. Since a maximum screening failure rate of 20% is expected, approximately 245 patients will be screened.
 
Mechanistic Sub-study
 
Any patient who consents can participate in the Mechanistic Sub-study. Patients with new-onset plaque psoriasis will be randomized to Arm A1b, Arm A2, or Arm B1b, those with chronic plaque psoriasis will be randomized to Arm C1 and Arm C2 (12 patients each). For Arm A1b or Arm B1b, the first 12 patients will be included on a first come first serve basis.

Key inclusion criteria
	
Patients eligible for inclusion in this study must fulfill all of the following criteria:
 
 1. Able to understand and communicate with the investigator, willing and capable to comply with all study procedures, and provide written signed and dated informed consent (personally or by a witness) before any assessment is performed 2. Aged 18 to 50 years inclusive 3. New-onset plaque psoriasis with appearance of the first psoriasis plaques within the last 12 months before randomization and naïve to any systemic treatment and phototherapy (Arm A1, Arm A2, and Arm B1). Episodes of mild psoriasis, which occurred at least 3 years before screening and resolved spontaneously within 6 months will be accepted 4. Chronic plaque psoriasis with appearance of the first psoriasis symptoms 5 years or longer and intolerance or inadequate response to phototherapy or any systemic treatment including biologicals, except for IL-17A inhibitors (Arm C1 and Arm C2) 5. Moderate to severe plaque psoriasis defined at screening and baseline by PASI \geq 10, and body surface area (BSA) \geq 10%, and IGA mod 2011 \geq 3

Key exclusion criteria
	
Patients fulfilling any of the following criteria will not be eligible for inclusion in this study:
 
 1. Forms of psoriasis other than plaque-type (e.g., pustular, erythrodermic, guttate, light sensitive, and drug induced) 2. Ongoing use of prohibited treatments 3. Previous treatment with phototherapy or any systemic treatment 4. Pregnant or nursing (lactating) women 5. Women of childbearing potential, defined as all women physiologically capable of becoming pregnant, unless they are using effective methods of contraception during the Treatment Epoch or longer if required by locally-approved prescribing information (e.g., 20 weeks in the EU and countries where applicable for secukinumab)

Study treatment	Secukinumab (AIN457) 300 mg Narrow-band UVB
Efficacy assessments	
 • Body surface area and psoriasis area severity index • Investigator's global assessment mod 2011
Safety assessments	
 • Physical examination • Vital signs • Height and body weight • Laboratory evaluations (hematology, clinical chemistry, high-sensitivity C-reactive protein) • Electrocardiogram (ECG) • Pregnancy • Adverse events
Data analysis	
The primary efficacy variable is the proportion of patients who achieve PASI 90 at Week 52. The analysis for the primary objective will be based on the full analysis set (FAS).
 
For the primary analysis, the following hypothesis testing will be performed:
 
$H_{01}: p_{\text{sec}} = p_{\text{nbUVB}}$ versus $H_{A1}: p_{\text{sec}} > p_{\text{nbUVB}}$
 
The primary analysis method for PASI 90 response at Week 52 will use a logistic regression model with treatment as an explanatory variable and significant covariates among baseline PASI score, age, and body mass index. The best subset of the significant covariates will be selected using a forward selection method. Interaction terms will also be considered, if significant, among the best subset of selected covariates and the treatment term.
 
The key secondary variable is the proportion of all randomized patients who achieve PASI 90 at Week 104. In order to reduce selection bias, all patients who do not achieve PASI 90 at Week 52 will also be included in the analysis at Week 104 using the PASI improvement obtained at Week 104 only.
 
For the key secondary analysis, the following hypothesis testing will be performed:
 
$H_{02}: p^*_{\text{sec}} = p^*_{\text{nbUVB}}$ versus $H_{A2}: p^*_{\text{sec}} > p^*_{\text{nbUVB}}$

Keywords	Psoriasis, IL-17A, secukinumab, narrow-band UVB, PASI

1 Introduction

1.1 Background

Psoriasis is an immune-mediated inflammatory disease (IMID) which may have a major impact on a patient's life, especially when its intensity is moderate or severe. There is evidence that treatment of psoriasis during the first years is conservative and frequently based on topical agents which rarely clear lesions completely. Treatment with biologic systemic agents is often initiated only when topical agents, phototherapy and conventional systemic treatment have proved to be inadequate, even in patients with moderate to severe disease (Maza et al 2012).

Psoriatic skin lesions are a "riot" of disorder, featuring dense inflammatory cell infiltrates, massive proliferation, impaired differentiation of the epidermis, formation of new blood vessels, and alterations in lymphatic structures. With effective therapy, psoriatic lesions resolve without scarring, which is remarkable, given the number of neutrophils in psoriatic skin lesions and the scarring observed in other neutrophil-mediated disorders, including pyoderma gangrenosum. Successful treatment of psoriasis leads to resolution of epidermal thickness, reduction in the number of inflammatory cells, and return of previously affected skin to a clinically normal state.

Once therapy is discontinued, psoriatic skin lesions tend to recur, usually at the same sites that were previously affected. Understanding and repairing the residual lesion in treated psoriatic skin may mean the difference between treating psoriasis and curing it.

There is evidence in other IMIDs (e.g., rheumatoid arthritis and Crohn's disease) that targeted systemic treatment, including biologics given early in the treatment pathway, may improve short- and long-term patient outcomes.

Both short- and long-term outcomes of early and intensive intervention in rheumatoid arthritis have clearly demonstrated benefits (Quinn et al 2005, Quinn et al 2012, van der Kooij et al 2009). In the BeSt study, 48% of the patients with initial intensive treatment with tumor necrosis factor alpha (TNF α) inhibitors and methotrexate could even stop the biologic treatment and remain in remission at year 4 of the study.

A patient-centered therapeutic approach, undertaken early in the psoriasis treatment pathway (early intervention) with the goal of complete clearance, may improve control of cutaneous symptoms and may also modify the course of the disease and the associated burden.

There is also evidence that – despite clinical clearance of psoriatic lesions – a subclinical inflammation may continue in the skin that may become clinical once treatment is stopped e.g., during or after a "drug holiday". A possible explanation for this phenomenon can be found in the identification of a T-cell subset called tissue resident memory T cells (T_{rm}) that has been proven to contribute to a tissue-localized immunological memory to viral infections of the skin (e.g., infections with herpes simplex virus).

This subtype of T cell has also been suggested to be a key player for generating chronicity of immune-mediated inflammatory or auto-reactive disorders like psoriasis (Clark 2015).

A newly published study identifies accumulation of IL-17 producing T_{rm} cells in the lesional or resolved skin of patients with psoriasis, which remain in the skin after resolution of lesions during treatment with biologic therapy, indicating the importance of this subset also in psoriasis

(Cheuk et al 2014). The presence of these cells in the skin may explain the chronicity of the disease and the reoccurrence of relapses to the same anatomic locations.

Cheuk et al (2014) also showed that T_{rm} cells in the psoriatic plaques produce interleukin (IL)-17A and IL-22 upon activation, supporting the notion of T_{rm} cells in psoriasis as Th17 cells with IL-17A as a key effector cytokine. In addition to the direct pathogenic effect of IL-17A from T cells on keratinocytes, IL-17A is also released by granulocytes and mast cells and plays an important role in early attracting more immune cells to the target organ.

Based on the increasing knowledge of the altered balance of T_{rm} cell subsets in psoriasis, inhibition of IL-17A early after disease onset may be a novel and important therapeutic approach interfering with the immune system before the establishment of extensive and chronic inflammation. This effect would be achieved in part by early blocking the recruitment of inflammatory cells, including Th17, and partly by blocking the key effector functions of T_{rm} cells.

Secukinumab is the first IL-17A inhibitor approved for the treatment of moderate to severe plaque psoriasis. It is hypothesized that early treatment with secukinumab in new-onset moderate to severe plaque psoriasis may both block recruitment of inflammatory cells and antagonize the effect of the key cytokine IL-17A produced by a subset of T cells.

1.2 Purpose

The purpose of this study is to determine whether early intervention with subcutaneous (s.c.) secukinumab 300 mg in patients with new-onset moderate to severe plaque psoriasis may lead to prolonged symptom-free periods by preventing reactivation of old lesions or ultimately totally hindering the occurrence of new lesions, i.e., changing the natural course of the disease (Main Study). New-onset psoriasis here is defined as psoriasis diagnosed within the last 12 months and not yet treated with systemic drugs or narrow-band ultraviolet light B (nb-UVB).

For the purpose of this study, early intervention with secukinumab will be compared with early intervention with nb-UVB.

In addition, a sub-study will be included, which aims to mechanistically understand the impact of early and late short- or long-term intervention with secukinumab on skin biomarkers (Mechanistic Sub-study).

2 Study objectives and endpoints

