4.1 Inclusion criteria

Patients eligible for inclusion in this study must fulfill all of the following criteria:

1. Able to understand and communicate with the investigator, willing and capable to comply with all study procedures, and provide written signed and dated informed consent (personally or by a witness) before any assessment is performed
2. Aged 18 to 50 years inclusive
3. New-onset plaque psoriasis with appearance of the first psoriasis plaques within the last 12 months before randomization and naïve to any systemic treatment and phototherapy (Arm A1, Arm A2, and Arm B1). Episodes of mild psoriasis, which occurred at least 3 years before screening and resolved spontaneously within 6 months will be accepted
4. Chronic plaque psoriasis with appearance of the first psoriasis symptoms 5 years or longer and intolerance or inadequate response to phototherapy or any systemic treatment including biologicals, except for IL-17A inhibitors (Arm C1 and Arm C2)
5. Moderate to severe plaque psoriasis defined at screening and baseline by PASI ≥ 10 , and BSA $\geq 10\%$, and IGA mod 2011 ≥ 3

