2.2.1 Subgroups of interest

The following subgroups of analysis will be explored for the primary and the key secondary analysis (Arms A1 and B1) :

- Weight (≤ 90 kg, >90 kg)
- BMI (< 25 , $25-< 30$, ≥ 30)
- Onset of psoriasis time (0-6 months, 6-12 months)
- Age ($< 18-30$, $31-50$)
- Concomitant medication in UVB arm (yes, no)
- Previous psoriasis therapy (biologic systemic therapy, non-biologic systemic therapy , Topical, phototherapy and Photochemotherapy – yes/no)

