2.3.2.2 Disease history and Baseline characteristics

In addition, the following variables collected at Baseline (Visit 1) will be summarized by treatment:

- 12-lead electrocardiogram (ECG)vital signs
 - sitting pulse (beats/min)
 - Mean of sitting blood pressure (systolic/diastolic) (mmHg)
- serum pregnancy test (only for women of child bearing potential)

█ [REDACTED]

█ [REDACTED]

- PASI total score
- PASI categories (< 10, 10 - ≤ 20, > 20)
- BSA (affected %)
- IGA mod 2011 score
- Time since the first diagnosis (by a physician) of plaque-type psoriasis (Years) (Visit 1 date is reference date)
- Presence of psoriatic arthritis (Yes/No)
- Time since the diagnosis of psoriatic arthritis (Years) (Visit 1 date is reference date)

Onset of psoriasis time in years will be calculated as:

Treatment start date - date of first diagnosis (by physician) of plaque psoriasis/psoriatic arthritis+1)/365.25

The first diagnosis date will be imputed according to the imputation rules in Section [5.3.3.3](#)

Visit 1 Date is nothing but treatment start date. If treatment start date is missing then randomization date will considered as a reference start date.

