5.3.3.3 First diagnosis date imputation

1. If the first diagnosis day/ month are missing and the year is non-missing:

- a. If the year part of the first diagnosis date is equal to the year part of the inform consent date, then the imputed first diagnosis date is set to the year start point (01JanYYYY).
- b. Otherwise the imputed first diagnosis date is set to the mid-year point (01JulYYYY).

2. If the first diagnosis day is missing and the month/year are non-missing:

- a. If the month and year part of the first diagnosis date is equal to the month and year part of the inform consent date, then the imputed first diagnosis date is set to the month start point (01MONYYYY).
- b. Otherwise the imputed first diagnosis date is set to the mid-month point (15MONYYYY).

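### The partial-date rule for first diagnosis ignores the 12-month new-onset limit, so a year-only date can give an eligible patient 12 to 18 months and no onset subgroup

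*Protocol*

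**What the plan says.** **The limit.** Protocol 1.2 defines new-onset disease by diagnosis: "New-onset psoriasis here is defined as psoriasis diagnosed within the last 12 months and not yet treated with systemic drugs". Inclusion criterion 3 (Protocol 4.1) sets the same 12 months by first lesions: "New-onset plaque psoriasis with appearance of the first psoriasis plaques within the last 12 months before randomization". Amendment 02 added one exception: "Episodes of mild psoriasis, which occurred at least 3 years before screening and resolved spontaneously within 6 months will be accepted".

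**The imputation.** SAP 5.3.3.3 covers partial first-diagnosis dates. If day and month are missing and the year is that of informed consent, "then the imputed first diagnosis date is set to the year start point (01JanYYYY". For any other year: "Otherwise the imputed first diagnosis date is set to the mid-year point (01JulYYYY". If only the day is missing and the month is not the consent month: "Otherwise the imputed first diagnosis date is set to the mid-month point (15MONYYYY". The rule is the same for new-onset and chronic patients.

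**Where the date goes.** SAP 2.3.2.2 derives time since onset as treatment start minus first diagnosis plus one day, divided by 365.25, and says: "The first diagnosis date will be imputed according to the imputation rules in Section" 5.3.3.3. SAP 2.2.1 lists, for Arms A1 and B1, the subgroup "Onset of psoriasis time (0-6 months, 6-12 months". There is no category above 12 months, and neither document says what happens to a derived duration above 12.

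**The concern.** The consent-year branch keeps the imputed date from falling after consent, so the rule respects the late end of the possible range. Nothing respects the early end, which for a new-onset patient is 12 months before randomization. Diagnosis normally follows the first plaques, so both protocol definitions imply that bound.

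A patient who met the entry criterion can therefore be given a duration that contradicts it and that has no place in the planned subgroup table. Other patients can be given a duration on the wrong side of 6 months. The 0-6-month group would be depleted and the 6-12-month group contaminated, which blurs any contrast between them and inflates mean disease duration at baseline.

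**Working it through.** The plan states no figure on this point, so there is none to reproduce. The check applies the rule to dates.

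**Inputs.** Imputation rule: SAP 5.3.3.3. Duration formula: SAP 2.3.2.2. Groups: SAP 2.2.1. Limit of 12 months: Protocol 1.2 and 4.1. Screening 1 to 28 days before baseline: Protocol 3.1. Assumed, because the documents give neither: treatment starts uniform over the year and true durations uniform up to 12 months.

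**1. Above 12 months (no distribution assumed).** Start 15 Oct 2018, diagnosis recorded only as 2017. The 12-month limit leaves 15 Oct to 31 Dec 2017, that is 9.5 to 12 months. The rule sets 1 Jul 2017: (471 + 1)/365.25 × 12 = 15.5 months. Any prior-year date with a start from July to December behaves this way, up to about 18 months at the end of December. A smaller route is consent in December and start in January: consent 20 Dec 2017, start 10 Jan 2018, diagnosis 1 Nov 2017 gives a true 2.3 months and an imputed 12.3.

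**2. Across the 6-month cut.** Start 15 Oct 2018, diagnosed 1 Sep 2018, year only: true 1.5 months, imputed from 1 Jan 2018 as 9.5.

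**3. Shares under the uniform assumption, consent equal to start.** Let R be the fraction of the year elapsed at start and d the true duration in years. The imputed duration is R if d < R, and R + 0.5 otherwise.
- Above 12 months: ∫ from 0.5 to 1 of (1 − R) dR = 0.125, or 12.5% of all. All of these are true 6-12-month patients: 0.125/0.5 = 25% of that group.
- True 0-6 moved to 6-12: 0.5 × 0.5 + ∫ from 0 to 0.5 of (0.5 − R) dR = 0.25 + 0.125 = 0.375; 0.375/0.5 = 75%.
- True 6-12 moved to 0-6: none.
- Mean imputed duration: ∫R² dR + ∫(R + 0.5)(1 − R) dR = 0.333 + 0.417 = 0.75 year, or 9.0 months against a true 6.0.
- Shortened: d > R + 0.5, giving ∫ from 0 to 0.5 of (0.5 − R) dR = 12.5% of all.

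**4. Calendar-day enumeration, year-only dates, by gap from consent to start.**

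| Gap (days) | True 0-6: stay / to 6-12 / above 12 | True 6-12: to 0-6 / stay / above 12 | All above 12 | All misplaced |
|---|---|---|---|---|
| 0 | 25.1 / 74.9 / 0.0% | 0.0 / 74.8 / 25.2% | 12.6% | 50.0% |
| 14 | 23.2 / 73.0 / 3.8% | 0.0 / 71.0 / 29.0% | 17.0% | 51.9% |
| 28 | 21.2 / 71.1 / 7.7% | 0.0 / 67.1 / 32.9% | 21.4% | 53.8% |

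**5. Dependence on start month (14-day gap).** The share of true 0-6-month patients moved to 6-12 is 97-100% for starts in July to December, but ranges from 9% to 81% for January to June and is below 50% in April to June.

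**6. Day-only missing.** About 3% are misplaced and the longest imputed duration is 12.5 months.

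**The case against.** The strongest case against is that few or no patients may be affected. Every percentage above is conditional on a year-only date, and the documents give no count. Criterion 3 must be checked against a 12-month window, and Protocol 8.1 requires full verification of adherence to the eligibility criteria. For a patient starting in July to December, a bare prior year cannot show that diagnosis fell inside the window, so sites would usually need at least the month. With the month known, the rule works almost as intended. This stands: any patient count would be a guess, and zero is possible. It does not remove the defect, because the SAP wrote a year-only branch and that branch gives impossible values when used.

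A second objection is that the consequence is small. Treatment is the randomized comparison, both main arms are new-onset, and early against late treatment is set by arm (A against C), not by this date. The rule is identical in A1 and B1, so it does not favour either treatment. This also stands.

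A third is that bounding at 12 months presumes eligibility. The FAS drops only misrandomized, untreated subjects (SAP 2.2 and 5.7), so a treated patient who breached criterion 3 stays in, and a blanket bound would impute that patient into compliance. The fix has to guard against this.

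**Conclusion.** The point holds as a defect in SAP 5.3.3.3 of minor weight. That eligible patients can be given 12 to 18 months follows from the rule alone. So does the one-way sorting from 0-6 to 6-12 months. The sizes (about 75% of true 0-6-month patients moved, about 12.5% of all above 12 months, or 13-21% with consent gaps up to 28 days) apply only to year-only dates and rest on uniform starts and durations. Affected outputs are the exploratory onset subgroups and the summaries of baseline duration.

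Three stronger readings are tempting and not supported:
- *Both branches always lengthen duration.* They do so on average. Diagnosis 1 Feb 2018, start 15 Jan 2019 with consent that January: true 11.5 months, imputed 6.5.
- *The primary or key secondary result is at risk.* Neither model uses time since onset; its covariates are baseline PASI, age and BMI.
- *Patients above 12 months are dropped from the subgroup analysis.* The SAP gives them no category but does not say how they are handled.

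**What to change.** In SAP 5.3.3.3, for Arms A1, A2 and B1, impute the midpoint of the feasible interval. Its start is the later of 01JanYYYY (or 01MONYYYY when the month is known) and randomization minus 12 months. Its end is the earlier of 31DecYYYY (or month end) and informed consent. Keep the present rule and flag the record if that interval is empty, if a deviation from criterion 3 is recorded, or if the date belongs to an accepted earlier mild episode. Leave the chronic arms unchanged. SAP 2.2.1 should then say how a flagged duration above 12 months is shown.

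In the first worked example the imputed value becomes about 10.7 months instead of 15.5. Under the same assumptions no bounded value exceeds 12 months (longest 11.99), and total misplacement falls from 50-54% to 25-26%. The bounded rule is not free of error: 25-37% of true 0-6-month patients still land in 6-12, and 18-25% of true 6-12-month patients now land in 0-6.

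The cost is a small programming change and a rerun of the onset-subgroup and baseline-duration outputs. The Week 52 and Week 104 main-study analyses have already been performed (SAP 2.14.1), so outputs already produced would change; the SAP introduction already provides for describing such changes in the CSR. Counting the year-only dates by arm first would show whether the rerun alters anything.
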